### Data analysis

**Enhancing reproducibility.** Instruments chosen are reliable and valid, although some gaming specific instruments are new, and this study will assess their psychometric properties (see below). Careful training of evaluators will precede study initiation, and assessment interviews will be audiotaped and rated for reliability when participants agree to taping (see Human Subjects; >90% of participants agree to taping in our trials). Evaluators blind to treatment conditions will conduct assessments, and obtaining information from multiple sources (parent and child) will allow for assessment of concordance between reports (see below).

**Primary aims.** We will examine baseline (BL) indices and other services received during treatment using the Treatment Service Review, and any differences between groups that relate to outcome can be used as covariates in subsequent analyses. Analysis will be conducted on an intent-to-treat basis, using all randomly assigned subjects. We will evaluate during treatment (BL to post-treatment) and longer-term (follow-up) effects.

**Aim 1:** To evaluate the feasibility and acceptability of this intervention, the proportion assigned to the intervention who complete all 6 sessions will be examined, as will parent and child ratings of satisfaction.

**Aim 2:** To examine the effect size of the intervention on reducing game playing days and durations of play, we will analyze TLFB data collected at each assessment period, with the greater report of parent or child

used for each day. Hierarchical linear models (HLM; Gibbons et al., 1993; Raudenbush & Bryk, 2002) will compare differences between groups over time. HLM is specifically designed for repeated measures designs with missing data, allowing for intra-subject serial correlation and unequal variance and covariance structures over time by incorporating available trend data for each individual with information on the group from which the subject is drawn. Maximum likelihood estimation enables analyses to be performed for the full trial without having to drop subjects with incomplete data, and both continuous and dichotomous variables can be analyzed. The model will include factors representing group, time, and their interaction, along with any important covariates.

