We will also compare proportions of subjects by group who are no longer gaming problematically, i.e., child reports no current DSM-5 IGD criteria and/or <5 criteria, and parent confirms no more problems for the most conservative approach. Logistic regressions will include important demographics and baseline indices of distress and severity of problems in Step 1. Step 2 will add treatment to determine if it adds unique variance in predicting outcomes after controlling for baseline indices.

**Power analyses.** This pilot is designed to assess feasibility, acceptability, and effect sizes. Thirty subjects per group are sufficient to address the former, to estimate effect sizes, and to detect moderately large differences of Cohen's (1988)  $d = 0.65$  with Type I error rate  $\alpha = .05$ , Type II error rate  $\beta = .20$ , and power  $[1 - \beta] = .80$ . If medium or larger effect sizes are noted, a larger randomized trial will be proposed to assess long-term efficacy.

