## 2. ADEQUACY OF PROTECTION AGAINST RISKS

### a. Recruitment and Informed Consent.

Informed Consent: A trained research staff member (Bachelors level or above), under supervision of the PI, will obtain informed consent. All potential subjects will receive an explanation of this study protocol, its potential risks and benefits, and alternative treatment available. Following resolution of any questions, parents/guardians and adult children (i.e., age 18) who agree to participate will be asked to sign the study

consent form and HIPAA document. A signed copy of the consent and HIPAA form will be given to each participant. Assent will be obtained from children under the age of 18, and both child and parent must agree to participate prior to collection of study data or randomization to a condition. As noted above, individuals who choose not to participate or who are deemed ineligible will be referred for other services as indicated.

An audiotaping section within the consent form will be utilized for recording of interactions between research staff and study patients, including baseline and follow-up interviews and therapy sessions. These audiofiles are utilized only for quality control procedures, to rate staff according to set standards in interview and treatment administration. Patients may participate in the study even if they do not choose to allow audiotaping (in our prior and ongoing studies, less than 5% of patients refuse audiotaping, and in this case both child and parent must agree or taping will not occur). The audiotaping consent section will explain that the purpose is to rate the staff member's interviewing and treatment administration skills.

b. Protection Against Risks. The following will protect against potential risks:

- i. Random group assignment is used, and about half of families will be assigned to the referral alone condition and half to the referral plus brief family behavioral therapy condition. These proportions will be outlined in the informed consent form, and patients will be made aware that they have about a 50% chance of being assigned to the family behavioral therapy condition. Patients may voluntarily end study participation if they are dissatisfied with their assignment.
- ii. The interviews and sample collections are brief, patients may skip questions or take a break if uncomfortable, and the particular instruments chosen are intended to minimize discomfort.

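### The logistic regression for remission has an open covariate set that exaggerates a non-null odds ratio in 60 families, and no rule for missing outcomes

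*Combined protocol and SAP*

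**What the plan says.** All of this is in the Data analysis section, and item 10 of the Detailed Data and Safety Monitoring Plan repeats the analysis text.

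- **Analysis set.** Under Primary aims: "Analysis will be conducted on an intent-to-treat basis, using all randomly assigned subjects".
- **Missing data.** The only mechanism is given under Aim 2, where the hierarchical linear model (HLM) is introduced for the gaming diary data: "Maximum likelihood estimation enables analyses to be performed for the full trial without having to drop subjects with incomplete data". The same sentence adds that "both continuous and dichotomous variables can be analyzed".
- **Remission.** It is analysed separately, in two steps. Step 1: "Logistic regressions will include important demographics and baseline indices of distress and severity of problems in Step 1". Then: "Step 2 will add treatment to determine if it adds unique variance in predicting outcomes after controlling for baseline indices". The child's report must be favourable, "and parent confirms no more problems for the most conservative approach", so both informants are needed to classify a family as remitted.
- **Size.** "Thirty subjects per group are sufficient to address the former, to estimate effect sizes". Allocation is about equal (Human Subjects, Protection Against Risks).
- **Status.** Item 2 of the monitoring plan makes remission a secondary analysis. It is also a stated expectation under the second specific aim.

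For the logistic model the plan gives no covariate list or maximum, assessment time, expected remission rate, small-sample method or rule for a missing child or parent report. The Approach section expects some appointments to be missed.

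**The concern.** Maximum likelihood estimates of a logistic coefficient are biased away from zero when the rarer outcome supplies few events per fitted parameter. Step 1 names three groups of covariates, each in the plural, before treatment enters. Primary aims also allows baseline differences related to outcome to be added. In 60 families this can become a heavily parameterised model, and the choice of covariates stays open until the data are seen.

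The second gap concerns who is analysed. The intent-to-treat statement covers all analyses, but the means of honouring it is described only for the HLM. A standard logistic fit leaves out any record without an outcome. Needing both reports makes that more likely. Families may also leave if they dislike their assignment (Human Subjects, Protection Against Risks), so loss could differ between arms.

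The pilot's purpose is to estimate effect sizes for a possible larger trial. An exaggerated remission odds ratio, or one from a selected subset, would be a poor planning input.

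**Working it through.** **The plan's own figure.** The only sample-size calculation is for a continuous outcome: 30 per group, d = 0.65, alpha .05, power .80. It reproduces with a one-sided test (power 0.800 by noncentral t) but not with a two-sided one (0.697); sidedness is not stated. It says nothing about the logistic model, so there is no stated figure to check there.

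**Inputs.** From the documents: 60 families, about 1:1. Assumed, because not given: overall remission 20% to 50% for the event counts; control remission 20% to 30% for the simulation; 3 to 9 covariates; 20% missing outcomes as an example, leaving 48 families.

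**Events per parameter** = (families × remission proportion) / (covariates + 1 for treatment).

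| Families | Remission | Events | 3 covariates | 9 covariates |
|---|---|---|---|---|
| 60 | 20% | 12 | 12/4 = 3.0 | 12/10 = 1.2 |
| 60 | 30% | 18 | 18/4 = 4.5 | 18/10 = 1.8 |
| 60 | 50% | 30 | 30/4 = 7.5 | 30/10 = 3.0 |
| 48 | 20% | 9.6 | 9.6/4 = 2.4 | 9.6/10 = 0.96 |
| 48 | 50% | 24 | 24/4 = 6.0 | 24/10 = 2.4 |

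**Simulated bias.** The model is logit(p) = a + log(OR) × treatment + 0.2 × (sum of independent standard normal covariates), with 1,500 trials per cell. The true odds ratio is conditional on the covariates, which is what the fitted model targets. Median fitted odds ratio for a true value of 3:

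| Families | Control remission | 0 covariates | 3 | 6 | 9 |
|---|---|---|---|---|---|
| 60 | 20% | 3.06 | 3.32 | 3.58 | 4.04 |
| 60 | 30% | 3.05 | 3.24 | 3.46 | 3.95 |
| 48 | 20% | 3.00 | 3.37 | 3.84 | 4.49 |
| 48 | 30% | 3.00 | 3.32 | 3.82 | 4.38 |

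- The excess is 8% (3.24/3) to 12% (3.37/3) with three covariates, and 32% (3.95/3) to 50% (4.49/3) with nine.
- With a true odds ratio of 1, the medians lie between 0.91 and 1.06: no systematic inflation.
- Stronger covariates (log odds ratio 0.3 each, eight of them) give 3.9 at 60 families and 4.2 to 4.5 at 48.
- Firth penalisation at 20% control remission gives 2.89 (60 families, six covariates), 2.83 (48, six) and 2.88 (48, nine).

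**Missing outcomes.** Take true remission of 25% (control) and 50% (therapy), so OR = (0.50/0.50)/(0.25/0.75) = 3.00. If a proportion r of remitters and n of non-remitters is lost, remission among those seen is p(1−r) / [p(1−r) + (1−p)(1−n)]. Baseline loss is 10%; the extra loss raises n to 30%.

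- Extra loss among therapy non-remitters: 0.45/(0.45 + 0.35) = 0.5625 against 0.25, OR 3.86.
- Extra loss among control non-remitters: 0.225/(0.225 + 0.525) = 0.30 against 0.50, OR 2.33.
- Extra loss among non-remitters in both arms: 0.5625 against 0.30, OR 3.00.
- 20% lost at random in both arms: OR 3.00. Counting those families as not remitted gives 0.40 against 0.20, OR 2.67.

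The risk difference is no more predictable. Suppose remission among those seen is 50% and 30%, and among those not seen 15%. The complete-case difference is 20 points. Among all randomised families it is:

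- loss of 30% in therapy and 10% in control: (0.7×0.50 + 0.3×0.15) − (0.9×0.30 + 0.1×0.15) = 11 points;
- loss of 20% in both arms: 0.43 − 0.27 = 16 points;
- loss of 10% in therapy and 30% in control: (0.9×0.50 + 0.1×0.15) − (0.7×0.30 + 0.3×0.15) = 21 points.

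**The case against.** A reader might infer three stronger statements. The documents support none of them.

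- **That the plan drops families with missing outcomes, contradicting intent-to-treat.** No section says so. Omission is the default behaviour of the method, and the plan is silent. The gap is an unsupported statement, not a contradiction.
- **That the model certainly has too many covariates.** Neither the number of covariates nor the remission rate is given. With three covariates the bias is modest, and small beside the sampling error of a 60-family trial.
- **That the remission effect will be overstated.** Small-sample bias needs a non-null effect, and loss of outcomes can act in either direction.

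It can also be said that remission is secondary. The decision to go further rests on medium or larger effects on gaming (end of Specific aims), and the primary gaming measures are playing days and duration, for which the HLM has stated missing-data handling. That is right and limits the severity. Remission nevertheless belongs to the second specific aim, and its estimate is the kind of result a later trial would plan from.

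Since the plan says its HLM can handle dichotomous outcomes, a mixed logistic model looks like the natural repair. It is not a good one here. A family missing both post-treatment and week 24 contributes no outcome information. The model also assumes outcomes are missing at random. Its odds ratio is subject-specific: for remission of 25% against 50%, an assumed random-intercept standard deviation of 1 turns 3.0 into 3.7, and 2 turns it into 5.9.

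**Conclusion.** The point holds as a weakness of method and a gap in specification. An ordinary logistic regression with demographics, distress and severity in about 60 families overstates a non-null odds ratio. For a true value of 3, the median is 3.2 to 3.3 with three covariates and 3.5 to 4.0 with six to nine; with 48 families it is 3.3 to 3.4 and 3.8 to 4.5. These figures rest on assumed control remission of 20% to 30%, the assumed covariate numbers and independent covariates of modest strength. There is no bias at an odds ratio of 1.

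Separately, nothing in the plan makes the intent-to-treat statement true for this model. The direction of any resulting bias cannot be stated in advance. Severity is low to moderate.

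**What to change.** In the Data analysis section and item 10 of the monitoring plan:

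1. Name the visit or visits at which remission is compared.
2. Replace the open Step 1 list with baseline IGD criteria count and the three stratification factors (child age group, sex, one or both parents participating). That is four covariates plus treatment, so 12/5 = 2.4 to 30/5 = 6.0 events per parameter in 60 families. This is still sparse, so the short list does not replace the next step.
3. Fit the model with Firth penalisation.
4. Report the risk difference between arms with its confidence interval beside the odds ratio.
5. Include all randomised families by multiple imputation, using baseline data and the other visits. As a sensitivity analysis, count missing outcomes as still IGD. Imputation also assumes missing at random, so the sensitivity analysis is needed. Do not rely on a mixed logistic model for this purpose.

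The cost is a few sentences and modest programming. Any odds ratio reported is likely to be somewhat less favourable than from the ordinary fit. No change to recruitment or assessments is needed.

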- 1. To evaluate the feasibility and acceptability of this intervention.** The proportion of participants who complete 6 sessions will be determined, along with parent and child satisfaction ratings of the treatment. We will consider the treatment feasible and acceptable if we are able to recruit the full sample and 70% or more of the families complete treatment and express moderate to high levels of satisfaction overall and with the majority of the session topics.

2. **To examine the effect size of the intervention in reducing gaming.** Parent and child reports of frequencies and durations of game playing will be compared over time between conditions to derive effect size estimates. We hypothesize that the behavioral family intervention will reduce the frequency and duration of game playing episodes relative to the control condition. We also expect that a lower proportion of youth in the intervention condition will meet current DSM-5 criteria for IGD following treatment.

Exploratory aims are to examine putative mechanisms of change including structural changes in the home environment, frequencies of monitoring gaming, participation in alternate activities, and family communication and functioning. If we can identify potential mechanisms of change for gaming behavior, we can focus subsequent psychotherapy development efforts on addressing those processes more directly.

We will also assess the effect size of the intervention on secondary outcomes including indices of substance use, attention problems, depression, sleep, psychosocial functioning and quality of life. We expect that the intervention will result in improvements along some or most of these domains if it yields benefits in reducing gaming.

In addition, we will evaluate concordance between parent and child reports on measures of gaming and gaming problems. These data will help inform development of diagnostic and assessment tools for IGD.

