### Approach

**Subjects** will be recruited by ads directed at parents, e.g., "Has your child developed problems from playing video games too much?" Staff will inform callers that the study involves both parent and child participation.

Inclusion criteria are: (1) parent/guardian of a 10-19 year old residing in the same household  $\geq 8$  months/year; and (2) child meets DSM-5 IGD criteria by self-report or by parent report (see below and Human Subjects).

Exclusion criteria are parent or child has a significant other mental health condition that may impact response to treatment (active suicidality, psychosis), and parent or child is unable to attend 6 sessions over 8 weeks.

Child age range spans early to late adolescence, and residential criteria ensure the child lives primarily with the target parent (allowing for visitation of divorced parents, but not boarding students). The child must meet DSM-5 IGD criteria via the self-reported or parent-reported VGDS or semi-structured interview. The self-report version of the VGDS has established psychometric properties (Rehbein et al., 2015) and we have found evidence of validity of the parent-version of the VGDS in our current pilot study, as evidence by concordance between the parent VGDS and a clinical interview administered by doctoral level clinicians.

**Informed consent.** Persons who call and appear eligible will be invited to an in-person assessment, at which we will obtain written informed consent from parents and children aged 18 years; those  $< 18$  will provide assent.

**Assessments.** Staff will administer instruments with established psychometric properties (when available) to assess study entry criteria, hypothesized mechanisms of action, and outcomes. Most measures will be collected at baseline (BL), week 4, post-treatment, and a week 24 follow-up. There are some exceptions. The demographic interview will be administered at BL only. The AUDIT, DUDIT, BRIEF, BIS-11 (parent and child versions), SRS, and the DERS will be administered at BL and post-treatment only. The SCID, TLFB, and the T-ASI will be administered at BL, post-treatment, and week 24 only. Abbreviated versions of some measures will be administered at the follow-ups. Some variability in the scheduling of the follow-ups will be allowed to account for variability between families in how quickly they complete the 6 sessions of therapy.

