**Exploratory aims** are to evaluate potential mechanisms of actions of the intervention including: changes in number and location of gaming devices in the home, frequency of monitoring child's game playing (via self reports in both groups, and confirmed by completed logs in Group B), child's participation in alternate activities (ACC), and parental rewarding of child behaviors and family communications (PSSS, BFAM scores). Following recommendations of Morgenstern and Longabaugh (2000) for assessing mediation, Model 1 examines whether the treatments engender differential outcomes on gaming indices (i.e., Aim 2 above). Model 2 will test if potential mediators change differentially over time by condition. For these analyses, a composite indicator for each construct will be utilized (e.g., summary scores of number/location of gaming devices, monitoring frequencies, ACC, PSS and BFAM scores). Model 3 will examine partial correlations between post-treatment scores on these indices and gaming outcomes, after controlling for baseline scores. If these three models show significant effects, the final model will assess associations between these variables and gaming outcomes. Step 1 of this model will include baseline scores of the potential mediator(s). In step 2, treatment group will be entered, and in step 3, post-treatment scores of the mediator(s) will be included, and resulting predictive power of treatment condition examined. If treatment is no longer significant and the post-treatment mediation term is significant, criteria for full mediation are met. Although we do not expect to find full mediation with this sample size, potential mediators with medium or higher effect sizes in Models 2-3 will be considered for future evaluation and inclusion in this intervention, if main effects of treatment are noted (Aim 2).

We will also assess effect sizes on secondary outcomes, e.g., substance use, psychosocial functioning and symptoms, sleep, and quality of life. HLM, outlined above, will compare groups over time on these indices.

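### The stated power (30 per group, d = 0.65, 80%) fits an undeclared one-sided t-test; a two-sided test at one time point gives about 70% power and a detectable d of 0.74

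*Combined protocol and SAP*

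**What the plan says.** The power paragraph under Data analysis states that "Thirty subjects per group are sufficient to address the former, to estimate effect sizes, and to detect moderately large differences" of Cohen's d = 0.65, with Type I error .05, Type II error .20 and power .80. Section 4 (Sample size) of the Detailed Data and Safety Monitoring Plan repeats it with the same figures. Neither copy says whether alpha is one- or two-sided, which test or time point is meant, how many measurements are credited, what correlation is assumed, or how much loss is allowed for.

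The rest of the plan bears on the figure as follows.

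- **Direction.** Aim 2 under Specific aims says: "We hypothesize that the behavioral family intervention will reduce the frequency and duration of game playing episodes relative to the control condition". This is a directional hypothesis. No section declares a one-sided test.
- **Allocation.** It is 1:1; "about half of families will be assigned to the referral alone condition and half to the referral plus brief family behavioral therapy condition".
- **Measurement times.** Under Approach, Assessments: "The SCID, TLFB, and the T-ASI will be administered at BL, post-treatment, and week 24 only". The gaming outcome therefore has one baseline and two later measurements.
- **Analysis.** The Aim 2 analysis is a hierarchical linear model (HLM). Both copies of the Aim 2 text say: "The model will include factors representing group, time, and their interaction, along with any important covariates". The Primary aims paragraph adds: "We will evaluate during treatment (BL to post-treatment) and longer-term (follow-up) effects".
- **Use of significance.** In the mediation plan Model 1 is the Aim 2 comparison, and "If these three models show significant effects, the final model will assess associations between these variables and gaming outcomes".

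**The concern.** An alpha of .05 with no sidedness given is normally read as two-sided. On that reading, 30 per group does not give 80% power for d = 0.65 in a simple two-group comparison. The planned HLM might recover the difference, but the power text is not linked to any of its contrasts, so a reader cannot check it.

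This figure is the only quantitative support offered for the sample size. Two things depend on it: the detectable effect that the plan advertises, and the chance of passing the significance gate to the final mediation model. The feasibility aim, the estimation aim and the decision to propose a larger trial, which rests on effect sizes, do not.

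**Working it through.** **Inputs from the documents.** n = 30 per group, 1:1; d = 0.65; alpha = .05; power = .80. Sidedness, contrast and correlation are not given.

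**Step 1. Reproduce the plan's figure.** For a two-sample t-test with SD 1, df = 58 and noncentrality = d × sqrt(n/2) = 0.65 × sqrt(15) = 2.517. Power is the probability that a noncentral t variable exceeds the critical value.

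- One-sided .05 (critical t = 1.672): power 0.800, detectable d 0.650, n = 30 per group. This matches the plan.
- Two-sided .05 (critical t = 2.002): power 0.697, detectable d 0.736. For d = 0.65, 38 per group gives 0.799 and 39 gives 0.809, so 39 per group (78 families) are needed.

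The normal approximation does not close the gap: two-sided power 0.711, detectable d 0.723, 38 per group.

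**Step 2. Ask whether the planned model could support d = 0.65 two-sided.** The documents give no correlation, so I assumed compound symmetry with correlation r between any two of the three measurement times, unit SD, d = 0.65 at both post-treatment and week 24, and complete data. For every row except group-by-time, the standardised effect shown replaces d in Step 1.

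| Two-sided contrast | Standardised effect | r = .3 | r = .5 | r = .6 | 80% power when |
|---|---|---|---|---|---|
| One time, baseline-adjusted (df 57) | d / sqrt(1 − r²) | 0.74 | 0.82 | 0.87 | r ≥ about 0.47 |
| One time, change from baseline (df 58) | d / sqrt(2(1 − r)) | 0.55 | 0.70 | 0.79 | r ≥ about 0.61 |
| Group-by-time, three times (2 and 116 df) | see below | 0.575 | 0.73 | 0.83 | r ≥ about 0.57 |
| Mean of both later times, change (df 58) | d / sqrt((1 + r)/2 + 1 − 2r) | 0.68 | 0.82 | 0.89 | r ≥ about 0.48 |
| Mean of both later times, unadjusted (df 58) | d / sqrt((1 + r)/2) | 0.87 | 0.82 | 0.79 | r ≤ about 0.56 |
| Mean of both later times, baseline-adjusted (df 57) | d / sqrt((1 + r)/2 − r²) | 0.91 | 0.94 | 0.96 | every r from 0 to 0.8 (minimum 0.91) |

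For the group-by-time F test, the noncentrality is (n/2) × Σ(δ_t − mean δ)² / (1 − r) with δ = (0, d, d). The sum is (2/3)d² = 0.2817, so at r = .5 the noncentrality is 15 × 0.2817 / 0.5 = 8.45 and power is 0.73.

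Simulations of 10,000 and 20,000 runs agreed. At r = .5, for example, they gave 0.816 for one time adjusted, 0.698 for one time change, 0.736 for group-by-time and 0.821 for the mean change.

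**Step 3. Effect of loss.** Although "Analysis will be conducted on an intent-to-treat basis, using all randomly assigned subjects", the power text makes no allowance for missing outcomes. With an assumed 10% to 20% loss (27 to 24 analysed per group), the single-time t-test has power 0.65 to 0.60 two-sided and 0.76 to 0.72 one-sided.

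**The case against.** The strongest reply is that nothing has been miscalculated. The figures reproduce under a one-sided test, which is compatible with the directional hypothesis, so the fault is incomplete reporting. The two-sided t-test at one time point is also my benchmark, not an analysis the plan specifies. Under the planned repeated-measures model some contrasts meet or exceed 80%, and the baseline-adjusted mean of both later times does so comfortably. Finally, this is a pilot aimed at feasibility and effect sizes. The one gate affected leads to an exploratory mediation model, and the plan already doubts that it will find full mediation with this sample.

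Much of this stands. The 70% applies only to the simple comparison, and the contrast table rests on compound symmetry and correlations that I supplied, whereas the model itself allows more general covariance. I do not claim that 80% is wrong for every HLM contrast. What does not stand is the inference that the statement can be left alone. A directional hypothesis does not declare a one-sided test. Some contrasts within the planned model, including baseline-to-post-treatment change and group-by-time, reach 80% only with a sizeable correlation. The plan printed an inferential power claim twice without the information needed to tell which case applies.

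**Conclusion.** The concern holds. The stated power matches a one-sided t-test that the plan does not declare. Read two-sided at one time point with complete data, 30 per group gives 70% power for d = 0.65, so a true effect of that size would be missed about 30% of the time instead of 20%, and the effect detectable with 80% power is d = 0.74. That the plan's authors used a one-sided calculation is inferred from the match; it is not documented.

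For the planned HLM the miss rate depends on a contrast and a correlation that are not named. The consequence is confined to the advertised detectable effect and the significance gate before the final mediation model. It should be fixed, but it does not threaten the study.

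**What to change.** Keep 60 families and reword the power paragraph in both places (Data analysis, and section 4 of the Data and Safety Monitoring Plan) in one of three ways.

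1. **Two-sided, simple comparison.** Suggested text: *Thirty families per group give 80% power to detect d = 0.74 (two-sided alpha .05, two-group comparison at one time point, complete data).* This is a conventional reference figure, so label it as such and not as the power of the HLM.
2. **One-sided.** Keep d = 0.65 and declare one-sided alpha .05 in both power paragraphs and in both copies of the Aim 2 analysis text.
3. **Two-sided, model-based.** Keep d = 0.65 but name the HLM contrast and state the assumed correlation. A single post-treatment contrast needs r of about 0.47 if baseline-adjusted, or 0.61 for change from baseline. For the mean of post-treatment and week 24, the baseline-adjusted contrast exceeds 80% for every r from 0 to 0.8, the unadjusted one needs r no higher than about 0.56, and the change contrast needs r of about 0.48. These thresholds rest on the Step 2 assumptions.

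Whichever is chosen, say whether complete data are assumed. The cost is two reworded paragraphs, or four under option 2. Recruitment, conduct and the rule for proceeding to a larger trial are unchanged.
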